Defined as $\text{SpO}_2 < 88\%$ in oxygen AND ≥ 1 of:

- Respiratory rate < 20 or > 100 breaths/min
- Apnoea requiring bag-mask ventilation
- HR < 100 or > 200 bpm

Major congenital malformation:

A malformation that is present at birth and which is incompatible with life or requires immediate surgical management

Severe jaundice:

Jaundice occurring within the first 24h after delivery and/or visible in sclera, palms or soles

PRIMARY OUTCOME

Early neonatal mortality:	Death of a neonate within the first 7 days after birth (day 0-6)
----------------------------------	--

SECONDARY OUTCOMES

Hypothermia:	Axillary temperature below the normal range (36.5°C – 37.5°C); can be subcategorised as follows: Mild: 36.0°C – 36.4°C Moderate: 32.0°C – 35.9°C Severe: <32°C
---------------------	---

Duration of hospital admission:	Mean time (days and hours) from hospital admission to discharge
--	---

Breastmilk feeding:	Process of feeding a mother's breastmilk to her infant, either directly from the breast or by expressing milk from the breast and feeding it to the infant by nasogastric tube, bottle, cup, or spoon, to provide calories, macronutrients, and micronutrients (10)
----------------------------	---

Time from intervention/control procedures starting to exclusive breastmilk feeding:	Mean time (days and hours) from initiation of intervention/control procedures to exclusive breast milk feeding
--	--

Neonatal mortality:	Death of a neonate within the first 28 days of life
----------------------------	---

Time from intervention/control procedures starting to clinical stabilisation:	Mean time (days and hours) from initiation of intervention/control procedures to clinical stabilisation, with stability defined as having met the following criteria for a continuous period of at least 24h: (i) Breathing spontaneously with SpO ₂ >90% in room air (ii) No need for supplemental oxygen or CPAP (iii) Respiratory rate 40 to <60 breaths per minute (iv) No apnoea (v) Heart rate 80 to <180 beats per minute (vi) Axillary temperature 36.0 to 37.4 degrees Celsius (vii) No need for IV fluids
--	---

Time from intervention/control procedures starting to death:	Mean time (days and hours) from initiation of intervention/control procedures to death
---	--

Frequency of readmission:	Mean frequency of episodes in which an infant who had been discharged from a hospital is admitted again during a defined time period

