1.4.2 Secondary outcomes

- Prevalence of hypothermia at 24 hours post-randomisation
- Mean duration of hospital admission (days and hours)
- Mean time from intervention/control procedures starting to exclusive breastmilk feeding (days and hours)
- Mortality within 28 days
- Time from intervention/control procedures starting to clinical stabilisation (days and hours)
- Time from intervention/control procedures starting to death (days and hours)
- Frequency of readmission
- Mean daily weight gain (g/day) at 28 days
- Infant-caregiver attachment at 28 days
- Women's well-being at 28 days

2. Background

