5.2 Screening

[figure not shown]
All new admissions to the newborn units at JH, IH, EH, KNRH and MH will be screened for eligibility by trained study staff. Eligibility will be assessed as soon as possible after admission and once the baby is aged 1h or older. This is in recognition of the large physiological changes that take place following delivery and that the stability of a newborn aged <1h may change rapidly and not accurately reflect the stability over the following 24h. All screening procedures will be performed by study nurses or medical research officers, with support from the study paediatrician at each site. Oral informed consent will be obtained from a parent/caregiver prior to the initiation of screening procedures.

Screening procedures will take place at the radiant heater or incubator where the neonate has been admitted in the following order:

1. Neonatal chronological age will be ascertained by questioning the parent/caregiver and/or examining the antenatal card, medical record, or referral notes.
2. Weight will be measured using the study scale (Seca) to ensure weight is $\geq 700\text{g}$ and $\leq 2000\text{g}$.
3. A focused physical examination will be conducted to assess for the presence of visually recognisable major congenital malformations, severe jaundice, and seizures.
4. A pulse oximeter with neonatal probe will be attached for continuous monitoring and documentation of HR and SpO₂ for an initial 10 minutes.

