5.6 Randomisation

Randomisation will take place following collection of necessary baseline data and before the intervention or control procedures start. The details of the randomisation method are outlined in section 3.2.1. In situations where both twins are eligible for enrollment, they will be allocated to the same arm.

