5.7 Intervention and Control Arms

After the completion of recruitment and randomisation procedures and any required medical procedures according to clinical care guidelines, neonates will be allocated to receive either the intervention or standard care.

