5.7.2 Delivering the control arm

Neonates allocated to the control arm will be placed in an incubator or under a radiant heater, as per standard management at the study sites. They will wear a hat and be wrapped as per standard care. Oxygen will be provided from an oxygen cylinder or concentrator and IV fluids will be securely attached via an IV cannula with drip rate calculated, as in the intervention arm. The pulse oximeter will be placed inside the incubator or next to the radiant heater. The parent/caregiver will be able to touch the baby, if

requested, but will not provide any skin-to-skin contact until he/she meets clinical stability criteria (see Section 3.2.5), which are consistent with those used in the WHO I-KMC trial and in line with standard clinical procedures at the study sites. Once stable, the baby can transition to routine (intermittent) KMC with the parent/caregiver in a chair or bed in the study area.

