10.2.2 Primary and secondary outcome analyses

The primary and secondary outcome analyses will be carried out on all neonates as randomised ('intention to treat'). Analysis will follow a pre-specified analysis plan approved by the TSC and DSMB prior to unblinding the study database. The criterion for statistical significance at the final analysis will be $P < 0.05$. The rate of loss to follow up will be reported. We will report risk ratios for mortality seven days after enrolment (primary outcome) and 28 days after enrolment (secondary outcome) for intervention versus control with associated 95% confidence intervals. Secondary outcomes: time from intervention/control procedures starting to death and length of hospital stay, will be analysed using Kaplan-Meier plots and the hazard ratios with accompanying 95% CI calculated using Cox proportional hazards regression. All other secondary outcomes will be analysed using appropriate regression models accounting for the nature of the distribution of the outcome and results will be presented as appropriate effect sizes with a measure of precision (95% confidence intervals). Both unadjusted analyses and analyses adjusted for stratification factors will be carried out. Additional exploratory analyses will control for any baseline measures that appear to be imbalanced between arms.

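### Time to death, clinical stabilisation and exclusive breastmilk feeding are timed from the start of procedures, a post-randomisation point that can fall later in the KMC arm and does not exist for some randomised babies

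*Protocol*

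**What the plan says.** **Origin.** The Definitions give one secondary outcome as "Mean time (days and hours) from initiation of intervention/control procedures to clinical stabilisation". They use the same origin for time to exclusive breastmilk feeding and time to death, and Section 1.4.2 repeats it for all three. Section 10.2.2 carries it into the survival analysis of death: "time from intervention/control procedures starting to death and length of hospital stay, will be analysed using Kaplan-Meier plots and the hazard ratios", the latter from Cox regression.

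**Order of events.** Section 5.6: "Randomisation will take place following collection of necessary baseline data and before the intervention or control procedures start". Section 5.7 then places delivery of either arm as follows: "After the completion of recruitment and randomisation procedures and any required medical procedures according to clinical care guidelines".

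**What starting means in each arm.** Section 5.2: "Screening procedures will take place at the radiant heater or incubator where the neonate has been admitted". Section 5.7.2: "Neonates allocated to the control arm will be placed in an incubator or under a radiant heater". Section 5.7.1 has KMC start promptly, with no stated maximum delay, after probes are attached and the baby is moved to the study area.

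**Recording.** The daily review in Section 6.1.2 lists the date and time at which skin-to-skin contact begins. It lists no matching start time for control procedures.

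**Analysis population.** Sections 10.2.2 and 10.2.4 require the primary and secondary analyses to include all neonates as randomised, whatever their adherence.

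**Other origins in use.** Section 1.4.2 has "Prevalence of hypothermia at 24 hours post-randomisation". Length of stay runs from admission (Definitions). Section 10.2.2 counts 7-day and 28-day mortality from enrolment.

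**The concern.** Randomisation is the last point at which the arms are comparable by design. A clock that starts later raises three problems.

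1. The gap between randomisation and time zero can differ by arm. A control baby already lies where control care is given. A KMC baby needs probes, a move and an available caregiver. Section 5.4.3 allows for a mother who is not immediately available, and Section 14.5 for mothers too ill to take part in the first 24 hours.
2. A baby who dies or is withdrawn before procedures start has no time zero. The protocol gives no rule for such a baby, yet requires every randomised baby in the analysis.
3. In the control arm it is unclear which event starts the clock, and no recording of it is listed.

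At stake are the estimates for three secondary outcomes. Time to stabilisation and time to feeding could differ between arms with no true effect. The hazard ratio for death could move in a direction that depends on how pre-start deaths are handled.

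**Working it through.** The protocol gives no delay and no hazard shape, so there is no plan figure to reproduce. Both are assumed below and shown as ranges.

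**Inputs from Section 10.1:** 25% control mortality (18% as the low case), 2188 babies, 1094 per arm. **Assumed:** no true effect, control clock at randomisation, KMC clock a fixed d hours later.

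**Step 1, stabilisation and feeding.** If T is the time from randomisation, the protocol analyses T − d. With no true effect the difference in means, KMC minus control, is −(d_KMC − d_control). A KMC-only delay of 0.5, 1 or 12 h therefore shortens the KMC mean by 0.5, 1 or 12 h.

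**Step 2, babies with no origin.** Take Weibull death times from randomisation, the same in both arms, with 25% dead at 168 h: S(t) = 0.75^((t/168)^k). Deaths before start are 1 − S(d). The share of 7-day deaths falling in the first 24 h is (1 − S(24))/0.25, which is 16%, 26% and 41% for k = 1, 0.75 and 0.5.

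- k = 1, d = 1 h: 1 − 0.75^(1/168) = 0.17%, about 2 of 1094.
- k = 0.5, d = 1 h: 1 − 0.75^(0.0772) = 2.2%, about 24 of 1094.
- d = 30 min: 0.09%, 0.37% and 1.56% for the three shapes, or 1 to 17 of 1094.

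**Step 3, hazard ratio for death** (Cox, follow-up to 168 h after randomisation, true value 1.00). Pre-start deaths are either kept as events at time zero or dropped.

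| KMC-only delay | Kept, k = 1 / 0.75 / 0.5 | Dropped, k = 1 / 0.75 / 0.5 |
|---|---|---|
| 0.5 h | 1.003 / 1.003 / 1.003 | 1.000 / 0.988 / 0.941 |
| 1 h | 1.007 / 1.006 / 1.006 | 1.000 / 0.981 / 0.917 |
| 4 h | 1.028 / 1.023 / 1.020 | 1.000 / 0.952 / 0.843 |
| 12 h | 1.088 / 1.070 / 1.055 | 1.000 / 0.905 / 0.745 |

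Hand check of the 12 h kept value at k = 1: the hazard is 0.28768/168 = 0.001712 per hour. Mean time at risk is 0.25/0.001712 = 146.0 h in control and (0.9797 − 0.75)/0.001712 = 134.1 h in KMC. The same deaths over less time give 146.0/134.1 = 1.09.

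At 18% mortality and 1 to 12 h, kept gives 1.005 to 1.084. At 1 h, dropped gives 1.00, 0.98 and 0.92 for the three shapes.

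**Step 4, longer follow-up.** Time to death carries no 7-day limit, and follow-up runs to day 28 to 30. Extending the same curve to 28 days, itself an assumption, gives at most 1.03 kept and 0.85 dropped (k = 0.5) at 12 h.

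**Step 5, scale.** Deaths: 0.25 × 2188 = 547. The standard error of the log hazard ratio is 2/√547 = 0.086, and ln(1.09) = 0.086, so the largest kept value is about one standard error.

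**Step 6, clock at randomisation.** Every baby has an origin. With the same null model and exponential delays of mean 1 to 12 h, the hazard ratio was 0.99 to 1.01 throughout.

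**The case against.** The strongest case on the other side is that this is a small matter of wording.

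- **Intention to treat is stated.** No section says that pre-start deaths are excluded, and a rule for a missing start time may sit in the analysis plan. This stands as to size: the kept column is the one that follows the protocol. It does not remove the conflict, because the origin is part of the written outcome definitions.
- **Delays should be short.** KMC is to start promptly, helpers may provide it (Sections 3.2.3 and 5.7.1), and a caregiver able and willing to provide it is an entry criterion (Section 4.2.1). This stands. Nothing supports a uniform 12 h gap.
- **Starting could be read to include probe attachment in the admission area**, so that the KMC clock begins before the move. That is possible, but it shows that the origin is undefined.
- **The endpoints are recorded coarsely.** Stability needs 24 continuous hours on 6-hourly checks, and full breastmilk feeding is recorded by date. A shift of under an hour is minor against that, although coarse recording does not cancel a systematic shift in a mean.

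A reader might infer that the rule would manufacture a survival benefit, citing the hazard ratio of 0.745. The documents do not support that. It needs pre-start deaths dropped against Sections 10.2.2 and 10.2.4, a fixed 12 h KMC-only delay, strong front-loading, and follow-up cut at 168 h. With the 81 dropped KMC deaths removed, the standard error is √(1/273.5 + 1/192.5) = 0.094, which puts that extreme case at 3.1 standard errors.

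Nor do two other passages establish the assumptions. Section 18 reports early deaths in another trial, counted from birth, whereas babies here enter at 1 to 48 h with severe instability excluded. The initiation-time bands in Section 10.2.3 state no origin.

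**Conclusion.** The point holds and is worth correcting, but its likely effect is modest. The origin of three secondary outcomes is a stated post-randomisation event. It can differ by arm, has no listed control recording, and is absent for a baby who never starts, so it cannot be squared with including every randomised baby.

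For stabilisation and feeding, any unequal delay passes straight into the comparison. For death, keeping all deaths gives a hazard ratio of about 1.00 with a prompt start and 1.01 to 1.09 for assumed delays of 1 to 12 h to 168 h, running slightly against KMC. Only dropping pre-start deaths together with a falling hazard favours KMC, for example 0.98 to 0.92 at 1 h. Larger distortions need delays that the protocol does not support.

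These sizes rest on assumed fixed delays in one arm, Weibull hazards, no true effect and 25% 7-day mortality. A reader might infer that the main result is at risk. It is not: the 7-day and 28-day mortality risk ratios and length of stay do not use this origin.

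**What to change.** In the Definitions, Section 1.4.2 and Section 10.2.2, time death, clinical stabilisation and exclusive breastmilk feeding from randomisation in both arms, as the protocol already does for hypothermia. State that every randomised baby enters these analyses, including those who die or are withdrawn before procedures start. Report the delay from randomisation to KMC start descriptively, as a process measure.

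The cost is rewording three outcome definitions and one analysis sentence. Allocation is revealed in RedCap (Section 3.2.1), so a randomisation time should be available; confirm that it is stored. The start of skin-to-skin contact is already collected (Section 6.1.2). No new data collection and no change to the sample size are needed.

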10.1 Sample Size

Surveillance data collected on admissions to the JH neonatal unit between January and December 2016 (Perinatal Audit Data from Uganda Paediatric Association) suggest that the mortality rate in the control arm will be at least 25% across the four sites. The most recent Cochrane review and a metaanalysis demonstrated large mortality reductions among stable neonates (RR 0.60 and 0.64 respectively) (2,3), and the RCT in Ethiopia published a RR for mortality amongst neonates before stabilisation of 0.57 (4). Assuming a conservative control mortality rate of 25% across the 4 hospitals in our study, 1750 neonates (875 per arm) would enable us to detect a relative difference between arms of 22.4% (5.6% absolute difference) with 80% power and a significance level of 5%. If the control mortality rate were in fact as low as 18%, we would still be able to detect a relative difference of 27% (absolute difference of 4.8%). We plan to recruit 2188 neonates (1094 per arm) in order to allow for 10% withdrawal due to clinical deteriorations and consent withdrawal, and 10% dilution due to

noncompliance and loss to follow-up. This sample size would enable us to detect absolute reductions of 6.3% and 5.4% from control rates of 25% and 18%, respectively, with 90% power. Results from the feasibility study suggest that ≥ 400 eligible neonates are admitted to JH per year. Preliminary data suggest ~ 500 eligible neonates each are admitted to IH and EH per year and ~ 800 eligible neonates are admitted to MH per year. Recruitment will take place over 24 months, leading to an eligible population of ~ 4400 neonates. Thus, we have applied a conservative recruitment rate of $\sim 50\%$ to achieve the target sample of 2188. The admissions audit data from our feasibility study suggest that a higher recruitment rate should be achievable. Recruitment will continue until the target sample is reached, up to a maximum of 27 months, which includes a 3-month buffer period in case recruitment is delayed or slower than expected.

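### Length of hospital stay is set for Kaplan-Meier and Cox with no rule for in-hospital death: the curve is wrong if deaths are censored, and the hazard ratio is distorted if death ends the stay

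*Protocol*

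**What the plan says.** Protocol section 10.2.2 handles two secondary outcomes in one sentence, time to death and stay: "length of hospital stay, will be analysed using Kaplan-Meier plots and the hazard ratios with accompanying 95% CI calculated using Cox proportional hazards regression". The same section sets the population: "The primary and secondary outcome analyses will be carried out on all neonates as randomised". Babies who die are therefore in the analysis of stay.

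The Definitions section describes the outcome as "Mean time (days and hours) from hospital admission to discharge". Section 1.4.2 lists it as "Mean duration of hospital admission (days and hours"), a mean and not a hazard.

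Section 10.1 expects that "the mortality rate in the control arm will be at least 25% across the four sites" and also considers a control rate of 18%. Section 1.2 hypothesises a 25% reduction in 7-day mortality with KMC.

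No section says whether an in-hospital death is censored, counted as the end of the stay, or treated as a competing event. Section 6.1.4 has the date and time of discharge or death recorded.

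**The concern.** Kaplan-Meier and Cox suit time to death, where the event can happen to every baby. They do not carry over unchanged to stay, because death removes a baby from any chance of discharge. The plan leaves two codings open within the named method.

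- **Deaths censored.** The Kaplan-Meier curve then treats babies who died as if they would later go home at the same rate as the others. One minus Kaplan-Meier is no longer the proportion discharged.
- **Death as end of stay.** An early death then counts as a short stay, so the arm with fewer deaths appears to stay longer.

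Death is common here and, if the trial's hypothesis is true, differs between arms. A reported effect on stay could then be partly or wholly an effect on survival. Deaths are also unlikely to be a random subset: section 10.2.3 gives mortality of 86% below 28 weeks and 41% at 28 to 31 weeks, and such babies may well stay longer if they survive.

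**Working it through.** **1. The plan's own figure.** Section 10.1 states that "1750 neonates (875 per arm) would enable us to detect a relative difference between arms of 22.4% (5.6% absolute difference"). With p1 = 0.25, p2 = 0.194, mean 0.222, two-sided 5% (sidedness assumed) and 80% power:

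n = [1.96·√(2·0.222·0.778) + 0.8416·√(0.25·0.75 + 0.194·0.806)]² / 0.056² = (1.1520 + 0.4935)² / 0.003136 ≈ 864 per arm.

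The plan has 875, where power is 80.5%. The mortality inputs are therefore taken as 25% and 19.4%, averaging (25 + 19.4)/2 = 22.2%. No figure is stated for stay.

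**2. Assumptions.** Only the median stay of 10 days comes from the protocol (section 2.4, 10 neonates, IQR 9 to 14). Timing of death, spread of stay and the link between risk of death and stay are assumptions. KMC is given no effect on any baby's own time to discharge.

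- Set A (400,000 babies per arm): log-normal stay, log-SD 0.4; exponential time to death, mean 3 days; correlation parameter linking severity and stay 0, 0.5 or 0.8.
- Set B (1,000 trials of 1,094 per arm): log-SD 0.33; time to death exponential with mean 2.5 days, capped at 7. In the frailty version a uniform risk score u multiplies the death probability by 3u² and the median stay by exp(1.2(u − 0.5)).

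**3. The curve with deaths censored.** With no link between death and stay, one minus Kaplan-Meier estimates the distribution of stay as if nobody died. At day 28 in Set A this is Φ(ln(28/10)/0.4) = Φ(2.574) = 0.995; in Set B it is Φ(ln 2.8/0.33) = 0.999. The proportion discharged alive by day 28 is far lower:

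| | 1 − Kaplan-Meier | Discharged alive, control | Discharged alive, KMC |
|---|---|---|---|
| Set A, no link | 99.5% | 76% | 81% |
| Set B, no frailty | 99.9% | 75.3% | 80.7% |

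The curve overstates discharge by about 19 to 25 percentage points and hides the difference between arms.

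**4. Mean stay if death ends it.** The artefact is roughly the difference in deaths times the gap between mean stay and mean time to death. In Set A, mean stay is 10·exp(0.4²/2) = 10.83 days, so 0.056·(10.83 − 3) = 0.44 days. In Set B, mean stay is 10·exp(0.33²/2) = 10.56 days and mean time to death is 2.5·(1 − e^−2.8) = 2.35 days, so 0.056·(10.56 − 2.35) = 0.46 days. The simulations give about 0.45 to 0.54 days (Set A) and 0.46 days (Set B, rising to 0.70 with frailty).

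**5. Hazard ratio for discharge.** Below 1 reads as a longer stay with KMC. Set B, 25% against 19.4% mortality:

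| Coding of death | HR, no frailty | HR, frailty | Trials significant at 5% |
|---|---|---|---|
| End of stay | 0.94 | 0.89 | 31% / 72%, longer stay |
| Censored | 1.00 | 0.94 | 1.5% / 25%, longer stay |
| Kept at risk, never discharged | 1.15 | 1.12 | 80% / 67%, shorter stay |

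Set A gives about 0.90 to 0.94, 0.95 to 1.00 and 1.11 to 1.14 for the three rows. At 18% control mortality and a risk ratio of 0.73, Set B gives 0.95/0.92, 1.00/0.96 and 1.13/1.11. With no mortality difference every hazard ratio is 1.00, so the departures come from mortality alone.

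**The case against.** The strongest reply is that Cox with deaths censored already is the cause-specific hazard ratio for discharge. The same sentence of section 10.2.2 plans a Cox hazard ratio for death, so both halves of a competing-risks report are there. This stands: the Cox model should not be removed. It holds only if deaths are censored, which the protocol does not say, and it does not rescue the Kaplan-Meier plot.

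A second reply is that coding of deaths belongs in the analysis plan, which section 10.2.2 announces and which is not shown. That is fair for the coding rule alone. But the protocol names Kaplan-Meier for this outcome, and under the more natural coding (death is not discharge) that plot is wrong. This is a badly fixed method and not merely absent detail.

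Third, the larger distortions need death coded as end of stay, and all the hazard ratios rest on assumed inputs. This also stands and limits how firmly the size can be stated.

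A reader might infer more than the documents support:

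- **That the analysis always counts against KMC.** It does not. The distortion can run against KMC, be absent, or favour KMC, depending on coding and frailty.
- **That the error passes into the cost-effectiveness result.** Section 10.3 does not feed the Kaplan-Meier or Cox result for stay into the economic model.
- **That a subdistribution hazard ratio is the cure.** It keeps babies who died at risk as never discharged (third row of the table) and departs from 1 by about 11% to 15% with no effect on stay at all.

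**Conclusion.** The point holds, for one secondary outcome; the primary outcome is untouched. As written, section 10.2.2 gives a misleading discharge curve if deaths are censored: over 99% by day 28 against about 76% and 81% discharged alive. That gap follows directly from the expected mortality and depends little on the other assumptions.

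If death is counted as end of stay, a mortality benefit alone yields a hazard ratio of about 0.90 to 0.94 and about half a day of extra stay. For scale, section 2.1 cites a reduction of 1.61 days with KMC, though in stable neonates. These figures rest on the assumed timing of death, spread of stay and frailty.

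With deaths censored the Cox hazard ratio is valid as a cause-specific measure. It can still lie at about 0.95 to 1.00 (0.94 in the frailty version of Set B) when KMC saves babies who then stay longer. It has to be read beside the mortality result, and relabelling it does not remove this.

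**What to change.** In section 10.2.2:

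1. Define the event for length of stay as discharge alive, with in-hospital death as a competing event.
2. Replace the Kaplan-Meier plot for stay with cumulative incidence (Aalen-Johansen) curves by arm, for live discharge and for death. Kaplan-Meier can stay for time to death.
3. Keep Cox as the cause-specific hazard ratio for discharge. State that deaths are censored and not counted as end of stay, and report it beside the cause-specific hazard ratio for death.
4. If a subdistribution hazard ratio is given, label it a combined effect on survival and discharge, not an effect on length of stay.
5. Reconcile this with the mean-duration wording in the Definitions and section 1.4.2. If a mean is kept, say in whom it is taken and how deaths enter.

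The cost is a change of wording and slightly more analysis work. The date and time of discharge or death are already recorded (section 6.1.4). The change should be settled before unblinding.
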